The DLT period is defined as the first 28-days (completion of 2 cycles). Upon the first occurrence of a delayed DLT (defined as any DLT that occurs between 4 to 6 weeks after administration of study drug) in any patient enrolled in Phase 1a dose escalation, all ongoing and subsequent DLT periods will be expanded to 42 days for all remaining and subsequent patients enrolled in Phase 1a dose escalation. If no patient experiences a delayed DLT, the DLT period will remain at 28 days for all patients. AST, CK, or LDH laboratory abnormalities without clinical sequelae are not considered a delayed DLT (see Section 3.1.2.1.1).

In the event that no MTD is identified and drug exposure exceeds those deemed necessary based on nonclinical pharmacology data or the clinical PK and PD data (if available), FivePrime and the Investigators may make a decision to discontinue dose escalation.

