### 3.1.2 Treatment Period

#### 3.1.2.1 Phase 1a Monotherapy Cohorts and Combination Dose Escalation Cohorts

Phase 1a consists of three cabiralizumab monotherapy cohorts and four dose-escalation cohorts of cabiralizumab in combination with nivolumab with a minimum of 3 patients enrolled in each cohort. The planned dose levels and schedules for the Phase 1a cohorts are as follows:

- Cohort 1aM1: 2 mg/kg cabiralizumab, q2w
- Cohort 1aM2: 6 mg/kg cabiralizumab, q2w
- Cohort 1aM3: 4 mg/kg cabiralizumab, q2w
  - (Dose was de-escalated to 4 mg/kg after DLT observed in 1aM2 (See Section 1.9))
- Cohort 1aC1: 1 mg/kg cabiralizumab + 3 mg/kg nivolumab, q2w
- Cohort 1aC2: 2 mg/kg cabiralizumab + 3 mg/kg nivolumab, q2w
- Cohort 1aC3: 4 mg/kg cabiralizumab + 3 mg/kg nivolumab, q2w
- Cohort 1aC4: 6 mg/kg cabiralizumab + 3 mg/kg nivolumab, q2w

The 2 mg/kg cabiralizumab monotherapy cohort (1aM1) was enrolled first, followed by enrollment in the 1 mg/kg cabiralizumab and nivolumab combination cohort (1aC1). Both cohorts cleared without any DLTs. The 2 mg/kg cabiralizumab and nivolumab combination cohort (1aC2) started after the DLT period cleared in the 1 mg/kg cabiralizumab and nivolumab combination cohort and 2 mg/kg cabiralizumab monotherapy cohort.

The 6 mg/kg cabiralizumab monotherapy cohort (1aM2) opened after the DLT period cleared in the 2 mg/kg cabiralizumab monotherapy cohort (1aM1). There were two DLTs in patients treated in the 1aM2 cohort, both due to laboratory abnormalities. Subsequently, the dose was de-escalated and Cohort 1aM3 (4 mg/kg cabiralizumab monotherapy) was opened. There were two DLTs in the 1aM3 monotherapy cohort and the protocol was subsequently amended to allow higher cutoffs for these laboratory values (see Section 1.8.1). Additional patients were added to the 1aM3 cohort to evaluate the DLT period under the new criteria.

The 4 mg/kg cabiralizumab and nivolumab combination cohort (1aC3) was opened after the DLT period cleared in the 1 mg/kg and 2 mg/kg cabiralizumab and nivolumab combination cohorts and in the respective cabiralizumab monotherapy cohorts.

The 1aM2 cohort was also re-opened with the new DLT criteria. Upon successful completion of the DLT period the 6 mg/kg cabiralizumab and nivolumab combination cohort (1aC4) may be opened.

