#### **3.1.2.1.1 Dose Limiting Toxicity**

A DLT is defined as a study drug-related  $\geq$  Grade 3 AE (using National Cancer Institute [NCI] Common Terminology Criteria for Adverse Events [CTCAE] v 4.03) occurring during the first 28-days, excluding: Grade 3 tumor flare (defined as local pain, irritation, or rash localized at sites of known or suspected tumor), Grade 3 rash, Grade 3 immune-related adverse event (irAE) that resolved to a Grade 1 or less within 14 days, or a transient (resolving within 6 hours of onset) Grade 3 infusion-related AE. Any recurrence of Grade 3 rash, Grade 3 immune-related AE, or Grade 3 infusion-related AE will be considered a DLT. An irAE is defined as a clinically significant AE that is associated with study drug exposure, of unknown etiology, and is consistent with an immune-mediated mechanism.

In the absence of clinical symptoms and other accompanying changes in bilirubin or ALT (as noted in appendices F, G, and H), serum elevations of AST/ALT  $> 12$  xULN and  $\leq 20$  xULN that last for  $< 7$  days will not be considered a DLT and serum elevations of CK and/or LDH  $> 15$  xULN and  $\leq 20$  xULN that last for  $< 7$  days will not be considered a DLT.

Upon the first occurrence of a delayed DLT in any patient enrolled in Phase 1a (defined as any DLT that occurs between 4 to 6 weeks after administration of study drug), all ongoing and subsequent DLT periods will be expanded to 42 days for all remaining and subsequent patients enrolled in Phase 1a dose escalation. If no patient experiences a delayed DLT, the DLT window will remain at 28 days for all patients.

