### **3.1.6 Stopping Rules**

#### **3.1.6.1 Stopping Rules for All Cohorts**

Management of drug-related toxicities will follow the adverse event management tables ([Appendix F](#) and [Appendix G](#)). Management of drug-related laboratory abnormalities will follow the management tables in Appendix H.

The Sponsor will discuss such cases with the study Investigators as appropriate to determine further enrollment. IRBs may be notified by the Investigators of all cases and decisions regarding continued enrollment, according to applicable regulatory requirements or institution procedures.

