#### 4.3.5 Dose Discontinuation Criteria for Cabiralizumab and Nivolumab

Discontinuation rules may be different for monotherapy and combination therapy and not all rules will apply to both arms of the study. [REDACTED]

Treatment of cabiralizumab in monotherapy or cabiralizumab in combination with nivolumab should be discontinued in the following cases unless otherwise specified:

- Any Grade 3 or higher uveitis *or* any Grade 2 drug-related uveitis, eye pain, or blurred vision that does not respond to topical therapy and does not improve to Grade 1 within the second re-treatment period *or* that requires systemic treatment
- Any Grade 3 or higher infusion-related reactions and hypersensitivity requiring discontinuation. Any re-initiation of therapy in this circumstance would require consultation with the Sponsor's Medical Monitor or designee.
- Any Grade 3 non-skin, drug-related AE lasting >7 days, including drug-related uveitis, pneumonitis, hypoxia, bronchospasm, and endocrinopathies with the following exceptions:
  - Grade 3 drug-related endocrinopathies adequately controlled with only physiologic hormone replacement do not require discontinuation
  - Grade 3 drug-related laboratory abnormalities do not require treatment

discontinuation except:

- Grade 3 drug-related thrombocytopenia >7 days or associated with Grade  $\geq 2$  bleeding requires discontinuation
- Any drug-related liver function test (LFT) abnormality that meets any one of the following criteria requires discontinuation:
  - ALT or AST >3x ULN **and** total bilirubin >2x ULN **or** INR > 1.5 xULN (in the absence of anticoagulation).
  - [REDACTED]
  - ALT or AST > 20x ULN (with or without concurrent liver metastases)
  - Total bilirubin >3x ULN (>5x ULN with concurrent liver metastases)
- Any Grade 4 drug-related AE or laboratory abnormality, except for the following events which do not require discontinuation:
  - Grade 4 neutropenia <7 days
  - Grade 4 lymphopenia or leukopenia <7 days
  - Isolated Grade 4 amylase or lipase abnormalities that are not associated with symptoms or clinical manifestations of pancreatitis. The Sponsor’s Medical Monitor or designee should be consulted for Grade 4 amylase or lipase abnormalities.
  - Isolated Grade 4 electrolyte imbalances/abnormalities that are not associated with clinical sequelae and are corrected with supplementation/appropriate management within 72 hours of their onset

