  - Grade 4 drug-related endocrinopathy AEs, such as adrenal insufficiency, adrenocorticotrophic hormone (ACTH) deficiency, hyper- or hypothyroidism, or glucose intolerance, which resolve or are adequately controlled with physiologic hormone replacement (corticosteroids, thyroid hormones) or glucose-controlling agents, respectively, may not require discontinuation after discussion with and approval from the Sponsor’s Medical Monitor or designee.
  - Grade 4 CK up to 20 xULN (in the absence of clinical sequelae)
- Any event that leads to delay in dosing lasting > 6 weeks from the previous dose requires discontinuation, with the following exceptions:
  - Dosing delays to manage drug-related adverse events are allowed. Prior to re-initiating treatment in a patient with a dosing delay lasting > 6 weeks from the previous dose, the Sponsor’s Medical Monitor or designee must be consulted. Tumor assessments should continue as per-protocol even if dosing is delayed. Periodic study visits to assess safety and laboratory studies should also continue per protocol, or more frequently if clinically indicated during such dosing delays or per the Investigator’s discretion.

- Dosing delays lasting > 6 weeks from the previous dose that occur for non-drug-related reasons may be allowed if approved by the Sponsor’s Medical Monitor or designee. Prior to re-initiating treatment in a patient with a dosing delay lasting > 6 weeks, the Sponsor’s Medical Monitor must be consulted. Tumor assessments should continue per protocol every 8 weeks ( $\pm 7$  days) even if dosing is delayed. Periodic study visits to assess safety and laboratory studies should also continue per-protocol or more frequently if clinically indicated during such dosing delays or per the Investigator’s discretion.
- Any AE, laboratory abnormality, or intercurrent illness which, in the opinion of the Investigator, presents a substantial clinical risk to the patient with continued cabiralizumab and/or nivolumab dosing
- Any drug-related Grade 3 or higher neurological toxicity
- Any Grade 3 or higher periorbital edema and persistent Grade 2 periorbital edema requiring 2 missed doses unless approved by Sponsor’s Medical Monitor
- Any Grade 3 or higher drug-related diarrhea or colitis, which does not resolve to Grade 1 or baseline within 28 days.
- Any Grade 4 skin toxicity
- Any Grade 4 renal toxicity
- Any drug-related Grade 3 or higher pulmonary toxicity

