## 6. Adverse Events

An *Adverse Event (AE)* is defined as any new untoward medical occurrence or worsening of a preexisting medical condition in a clinical investigation, patient-administered study drug and that does not necessarily have a causal relationship with this treatment. An AE can therefore be any unfavorable and unintended sign (such as an abnormal laboratory finding), symptom, or disease temporally associated with the use of study drug, whether or not considered related to the study drug.

The causal relationship to study drug is determined by an investigator and should be used to assess all AEs. The causal relationship can be one of the following:

- Related: There is a reasonable causal relationship between study drug administration and the AE.
- Not related: There is not a reasonable causal relationship between study drug administration and the AE.

The term “reasonable causal relationship” means there is evidence to suggest a causal relationship.

AEs can be spontaneously reported or elicited during open-ended questioning, examination, or evaluation of a patient. (In order to prevent reporting bias, patients should not be questioned regarding the specific occurrence of one or more AEs.)

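### In the visible text, the lower bounds of the laboratory DLT exemption (AST/ALT >12, CK/LDH >15 xULN) serve no purpose: they invert the rule if Grade 3 starts below them and do nothing otherwise

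*Protocol*

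**What the plan says.** Protocol Section 3.1.2.1.1 defines a DLT as a drug-related event of Grade 3 or higher (CTCAE v4.03) in the first 28 days. It excludes Grade 3 tumor flare, Grade 3 rash, Grade 3 immune-related events that settle to Grade 1 or lower within 14 days, and Grade 3 infusion events that resolve within 6 hours.

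The next paragraph adds a laboratory exclusion, for use when there are no symptoms and no accompanying bilirubin or ALT changes, with a pointer to Appendices F, G and H. It has two bands, joined by "days will not be considered a DLT and serum elevations of CK and/or LDH":

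- AST/ALT above 12 and up to 20 xULN, for less than 7 days
- CK and/or LDH above 15 and up to 20 xULN, for less than 7 days

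Section 3.1.2.1 gives the history. After laboratory DLTs in 1aM2 and two further DLTs in 1aM3, "the protocol was subsequently amended to allow higher cutoffs for these laboratory values". It adds: "The 1aM2 cohort was also re-opened with the new DLT criteria".

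On delayed DLTs (weeks 4 to 6), which extend the DLT window to 42 days, the synopsis states that "AST, CK, or LDH laboratory abnormalities without clinical sequelae are not considered a delayed DLT" and cites Section 3.1.2.1.1. The delayed-DLT paragraph there counts any DLT in that interval and contains no such sentence.

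**The concern.** An exemption for transient, asymptomatic laboratory rises needs a ceiling, above which the rise is too large to ignore. This one also has a floor. No visible text says how a Grade 3 rise at or below the floor is classified, so the base definition applies and the rise is a DLT unless another exclusion catches it. That would penalise the milder of two otherwise similar events.

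DLT incidence, including laboratory abnormalities defined as DLTs, is a Phase 1a primary endpoint (Protocol Section 7.3.1.1) and drives escalation (Section 3.1.2.1). Cohort 1aM2 (6 mg/kg) was re-opened under the amended criteria, and its DLT period gates 1aC4.

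The delayed-DLT mismatch is a separate point. The two texts give different answers on which laboratory events start the 42-day window for all ongoing and later escalation patients.

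**Working it through.** The plan gives no figure to reproduce. The check is of the rule's logic.

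**Inputs**

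- Floors 12 (AST/ALT) and 15 (CK/LDH), ceiling 20 xULN, duration under 7 days: Protocol Section 3.1.2.1.1.
- T, the xULN value above which an event is Grade 3: not printed in either document, so it is varied. LDH shares the CK floor, but nothing is assumed about how LDH is graded.
- Exposed events: isolated, asymptomatic rises that are drug-related, recorded as an adverse event of Grade 3 or higher, and not excluded as a resolving immune-related event. Section 6 lets an adverse event be "any unfavorable and unintended sign (such as an abnormal laboratory finding". Section 6.4 asks for capture mainly when a result is clinically significant, serious, interrupts or stops treatment, or needs corrective therapy.

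**Rule as written**

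DLT if value > T, unless floor < value ≤ 20 and duration < 7 days.

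**Case 1, T below the floor.** A value v1 with T < v1 ≤ floor is a DLT at any duration. A value v2 with floor < v2 ≤ 20, for less than 7 days, is not. So v2 > v1, yet only v1 counts. With T = 5 assumed, AST of 9 xULN for 3 days is a DLT and AST of 18 xULN for 3 days is not. With T = 10 assumed, the same holds for CK of 11 against 18 xULN.

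**Case 2, T at or above the floor.** Values at or below the floor are not Grade 3, so the floor excludes nothing.

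Width of the non-exempt band under the floor, max(0, floor − T), in xULN:

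| Assumed T | 3 | 5 | 8 | 10 | 12 | 15 |
|---|---|---|---|---|---|---|
| AST/ALT (floor 12) | 9 | 7 | 4 | 2 | 0 | 0 |
| CK (floor 15) | 12 | 10 | 7 | 5 | 3 | 0 |

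Over whole-number T from 1 to 24, the AST/ALT rule is inverted for T = 1 to 11 and for no T from 12 up. The CK rule is inverted for T = 1 to 14 and for no T from 15 up. If Grade 3 includes its own threshold value, one boundary point is added at T equal to the floor. With the floors removed there is no inversion at any T, and the only results reclassified are those above T, at or below the floor, and shorter than 7 days.

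**What one extra counted DLT does** (synopsis and Section 3.1.2.1)

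- 0/3 to 1/3: escalation becomes three more patients.
- 1/6 = 16.7% to 2/6 = 33.3%: escalation becomes expansion to nine.
- 3/9 = 33.3% to 4/9 = 44.4%: the dose exceeds the MTD. If 33.3% is itself read as above 33%, this step is 2/9 = 22.2% to 3/9.

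**Illustration only.** Assume a 10% rate of other DLTs and a share q of patients with a counted rise under the floor, so p = 1 − 0.9(1 − q). Assume also that 3/9 is accepted and that the optional expansion after 2/3 is always taken. With b(n,k) the binomial probability at p,

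P(clear) = b(3,0) + b(3,1)b(3,0) + b(3,1)²[b(3,0)+b(3,1)] + b(3,2)[b(6,0)+b(6,1)].

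At q = 0, p = 0.10: 0.7290 + 0.1771 + 0.0574 + 0.0239 = 0.987. At q = 10%, 20% and 30% it is 0.916, 0.768 and 0.567. If 3/9 is rejected, the four values are 0.964, 0.829, 0.630 and 0.425. The documents give no value for q.

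**Delayed DLT, side by side.** The synopsis exempts AST, CK and LDH abnormalities without sequelae, with no bounds and no duration limit, and does not name ALT. Section 3.1.2.1.1, which it cites, offers only the bounded, under-7-day exemption. An asymptomatic CK rise above 20 xULN in week 5, if drug-related and Grade 3 or higher, opens the 42-day window under one text and not under the other.

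**The case against.** The strongest reply is that the defect depends on text that cannot be seen. The Grade 3 threshold is not printed. Section 1.8.1, cited for the amended cutoffs, and Appendices F to H, named in the exemption sentence itself, are withheld. Section 3.1.6.1 says: "Management of drug-related laboratory abnormalities will follow the management tables in Appendix H". SAP Section 7.6.7.1 reports ALT/AST >5 to ≤12 xULN with bilirubin ≤2 xULN next to a >12 to ≤20 tier with the same bilirubin condition, which fits a lower tier handled elsewhere. A move to higher cutoffs can also mean that the band is the range added and that lower values were already exempt. All of this stands, and it keeps the point conditional. A reader might infer that the plan has no rule for lower values. The documents do not support that, because withheld text is not absent text.

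It does not remove the point. Section 3.1.2.1 and the synopsis send DLT determination to Section 3.1.2.1.1. The appendix pointer there attaches to the accompanying bilirubin or ALT changes, and Section 3.1.6.1 describes the appendices as management tables. If a lower tier exists, it belongs in the definition.

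Some supporting evidence is only indirect. The discontinuation rules in Section 4.3.5 use the same ceiling with no floor ("ALT or AST > 20x ULN (with or without concurrent liver metastases" and "Grade 4 CK up to 20 xULN (in the absence of clinical sequelae"), but they govern stopping treatment, not DLTs. The CK line implies that Grade 4 CK begins below 20 xULN. It does not show that Grade 3 begins below 15. The synopsis sentence governs a different trigger, so it does not contradict the 28-day rule, but it does disagree with the section it cites.

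The immune-related exclusion may catch some rises under the floor. It requires a clinically significant event consistent with an immune mechanism, and it covers Grade 3 only. An isolated asymptomatic rise does not clearly qualify, and Grade 4 does not qualify at all.

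**Conclusion.** The point holds in conditional form and is minor. In the visible text the floors have no useful function at any Grade 3 threshold: they invert the rule when T is below 12 (AST/ALT) or 15 (CK), and are redundant otherwise. The inversion compares two rises that both last under 7 days. It rests on two assumptions: that Grade 3 starts below the floor, and that no withheld text exempts lower values.

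The direction is conservative: extra DLTs slow or stop escalation. A reader might infer a safety risk, or that the wording misclassified a patient or altered a dose decision. The documents support neither. The two original 1aM2 DLTs came before the amended criteria, 1aM3 and 1aC3 are reported as cleared, and the SAP plans summaries for 1aC4. How often a rise under the floor occurs cannot be estimated.

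The delayed-DLT mismatch between the synopsis and Section 3.1.2.1.1 is visible whatever T is.

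**What to change.** Apply prospectively:

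- In Section 3.1.2.1.1, keep the opening condition on symptoms and on bilirubin or ALT changes, with its appendix reference, and replace the two bands by AST/ALT ≤20 xULN, or CK and/or LDH ≤20 xULN, lasting <7 days. The bilirubin/ALT condition must stay. Without it, a rise with raised bilirubin would be exempted.
- If an appendix or Section 1.8.1 sets a different rule for lower values, state that rule in Section 3.1.2.1.1 instead.
- Give the synopsis and Section 3.1.2.1.1 the same laboratory rule for delayed DLTs, including whether ALT is covered and whether the 20 xULN and 7-day limits apply.
- Leave recorded DLT counts unchanged.

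The cost is one amended paragraph and one aligned synopsis sentence. The downside is that slightly fewer laboratory events count as DLTs in later patients.

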### **3.1.2.2 Phase 1a Extended Treatment Period**

Upon completion of the DLT period, patients from the Phase 1a monotherapy and combination cohorts may participate in an Extended Treatment Period.

Patients from the Phase 1a monotherapy cohorts are allowed to continue to receive cabiralizumab monotherapy at the same cabiralizumab dose level and patients from the Phase 1a combination cohorts are allowed to continue to receive cabiralizumab in combination with nivolumab at the same dose levels until disease progression, unacceptable toxicity, or other reason for treatment discontinuation.

### **3.1.2.3 Phase 1a 3-week Dosing Regimen Cohort**

In protocol amendment 4, a 3-week dose regimen cohort (1aD) is added to characterize the PK profile and safety of cabiralizumab in combination with nivolumab when administered as an alternative dosing schedule. This Phase 1a 3-week Dosing Regimen consists of one cohort evaluating 4 mg/kg cabiralizumab in combination with 3 mg/kg nivolumab, administered intravenously every three weeks until disease progression, unacceptable toxicity, or other reason for treatment discontinuation.

### **3.1.2.4 Phase 1a Exploration Cohorts**

The Phase 1a exploration consists of up to 40 additional patients to further evaluate the safety, PK, and PD of cabiralizumab as monotherapy and in combination with nivolumab.

### **3.1.2.5 Phase 1b Expansion Cohorts**

To further characterize safety and efficacy of cabiralizumab in combination with nivolumab, Phase 1b will enroll up to 7 expansion cohorts in 6 advanced cancer types (1b1 through 1b7). Enrollment in Phase 1b will begin when an RD has been identified based on overall safety, tolerability, PK, and PD (if available) data.

During enrollment of any expansion cohort, if the observed number of responses makes it unlikely to achieve a target response rate for that indication, then further recruitment to that cohort may be suspended or terminated.

After initiation of Phase 1b, the dose may be changed based on data from continued dose exploration in Phase 1a. There will be no intra-patient dose modification and any alteration in dose for Phase 1b will only apply to newly enrolled patients in Phase 1b.

## **3.1.3 End-of-Treatment Follow-up Period**

All patients should return to the clinic 28 ( $\pm 7$ ) days and 100 ( $\pm 7$ ) days from their last dose of study drug to complete the End-of-Treatment Follow-up Period, irrespective of whether a patient is discontinued from the study drug at a planned visit or mid-cycle. AEs will be assessed until resolution, return to baseline, or are stabilized per treating Investigator's assessment. Adverse

event reporting will continue until 100 ( $\pm 7$ ) days after the last dose of study drug or until initiation of subsequent anti-cancer therapy.

